Aim 1: Adapt and refine the integrative components of the FIT Teens intervention to develop a new culturally tailored I-STRONG intervention for youth with chronic SCD pain. We will conduct mixed method approaches and purposive sampling to collect qualitative feedback informed by patient and family lived experiences regarding intervention content, format, perceived benefits, and barriers/facilitators to engagement from 15 patients (12-18 years) with chronic SCD pain and their parents and about 8 adolescents and 8 parents to participate in stakeholder advisory boards. Community stakeholder advisory boards and iterative design will inform intervention adaptation and refinement to enhance clinical implementation.

Aim 2: Assess feasibility and acceptability of I-STRONG intervention for youth with chronic SCD pain. We will conduct a single-arm proof-of-concept study of the I-STRONG intervention with 12 adolescents (12-18 years) to iteratively optimize the feasibility and acceptability of I-STRONG in youth with chronic SCD pain. Feasibility will be demonstrated by rates of study enrollment, retention, and adherence (target goals set at $\geq 75\%$). Acceptability will be demonstrated by treatment burden, satisfaction, and tolerability. Qualitative feedback about the program format and content will inform additional intervention optimization, refinement, and enhance feasibility and acceptability.

3. Background

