Week 7	Session 13 (T)	Problem solving, Improving communication about pain	Begin Level 4 Functional movement
	Session 14 (T)	Maintenance Planning (Pain Action Plan)	Level 4 Functional movement
Week 8	Session 15 (P, T)	Review skills and progress with parents	Level 4 Functional movement
	Session 16 (P, T)	Review Pain Action Plan and problem solving	Level 4 Functional movement; Introduction to home practice

Adaptation and Optimization of Treatment Manual: Intervention content, delivery style, and

materials will be adapted for optimization based on analyses of qualitative feedback from semi-structured interviews, theater tests, and our interdisciplinary team of experts (draft 1). We will seek feedback on the treatment protocol from 5 external topical experts, such as patient and caregiver stakeholders as well as physicians and behavioral scientists with significant expertise in SCD pain, pediatric chronic pain, and mind-body interventions, which will be integrated for adaptation (draft 2). Readability testing (Flesch-Kincaid) will be applied to ensure protocol content is below a fourth-grade reading level to enhance health literacy, comprehension, and facilitate use and acceptability (draft 3). The treatment manual will then be ready for preliminary testing and optimization in Aim 2.

Aim 2. We will use mixed-method approaches using administration of questionnaires, semi-structured interviews, performance-based assessment (i.e., 6-minute walk test), and ecological momentary assessment via actigraphy to optimize I-STRONG for SCD. We will conduct 2-3 groups of 4-6 patients in each group with protocol refinements and optimization after completion of each group. Additional groups may be conducted to optimize feasibility and acceptability.

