Study Intervention Adherence. Adherence to treatment will be assessed based on patient attendance at treatment sessions and patient self-report of home practice of mind-body, cognitive-behavioral, and movement skills. Participants who miss sessions will have the opportunity to catch up individually with their coaches prior to the next group session (e.g., 30 minutes before the next session for patient and/or parent who missed previous session) to ensure timely delivery of intervention content to all group members. Participants will not be integrated into a different group to ensure maintenance of group cohesion. If a patient is hospitalized during the treatment phase and there are no medical contraindications for their participation in treatment sessions, patients will be provided an opportunity to participate in sessions to the extent possible (e.g., join via iPad to learn mind-body or cognitive-behavioral strategies and observe or modify neuromuscular movement to their ability).

Semi-structured qualitative exit interviews. At the end of the treatment program, caregivers and patients will be asked for feedback in separate one-on-one interviews lasting up to 90 minutes. The interviews will elicit participants' impression of the program, how well they could do mind-body, cognitive-behavioral, and movement skills in session, feedback about the difficulty level of movement and progression of movements. Participant feedback about content and format of sessions will also be solicited including how they liked the program, how well the content was integrated, interest level, length of sessions and format, size and cohesion of group-based sessions, and any suggestions or changes to the materials or format. Information from these interviews will be used to refine and optimize I-STRONG for SCD. Interviews will be conducted by telehealth and will be audio recorded as digital files and transcribed for analysis.

Stakeholder Advisory Boards: We will reconvene our existing patient and caregiver advisory boards assembled to support the intervention adaptation to review qualitative feedback from exit interviews and proposed intervention adaptation and refinements. An iterative process allows for continued optimization to ensure feasibility and promote acceptability(15).

7. Sharing of Results with Participants

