will also contact participants in their research database who have agreed to be contacted for future studies either with a phone call, mailed letter and infographic describing the study in a “who, what, where, and why” format, or in-person during scheduled clinic visits. Mailed letters will be followed up with a personal phone call to the family to describe the study in further detail and determine interest and eligibility. All potentially eligible patients will be approached and screened during their routine outpatient SCD appointment. If youth and caregivers are interested in learning more, study staff will provide details, opportunities for questions, and seek informed consent and assent. Designated research coordinators who are racially representative of the patient population will conduct screening procedures and remain the primary research study contact during the family’s study participation. We will track the number of eligible patients screened by phone or in-person, enrolled, and reasons for refusal.

We will use purposive sampling to recruit a representative sample of a broad patient population based on patient age, sex, SCD genotype, national origin (e.g., African, Caribbean, African American), and family socioeconomic status. Our sites have used the following strategies to achieve 80-95% recruitment rates for qualitative interview participation and proactively manage scheduling challenges: (1) survey families for good dates/times; (2) schedule sessions virtually or at hospital campus locations closest for families; (3) obtain endorsement from trusted medical staff; (4) respectful face-to-face, phone, and written communication from consistent study team members highlighting the importance of family involvement to improve SCD care; (5) transportation vouchers and child care during interviews to allow sustained attention and participation; (6) meals and/or activities to engage all family members; and (7) anticipate facilitators/barriers to participation to refine planning and marketing strategies (46). We will optimize these recruitment strategies based on iterative stakeholder feedback.

Iterative patient, parent, and community expert stakeholder engagement through qualitative interviews and advisory board involvement will optimize and enhance these retention strategies:

- Identify 2 contact persons knowledgeable of participants’ updated contact information to minimize loss to follow-up due to relocation

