Feasibility will be characterized with descriptive statistics (means, standard deviations), frequency counts, and percentages to determine enrollment (percent of eligible participants that consent), retention rates (percent of patients completing the study at primary endpoint of 3-months follow-up), completion of primary outcome assessments (percent of primary outcome assessments completed), and treatment completion (percent of planned or makeup treatment sessions completed). We anticipate with iterative refinement to achieve the following target goals: $\geq 30\%$ of eligible patients approached will consent, $\geq 75\%$ retention rates, $\geq 90\%$ completion of primary outcome assessments at 3-month follow-up assessment (primary endpoint), and $\geq 75\%$ treatment completion (attending at least 75% of planned or makeup sessions). Treatment engagement will examine the rate of homework completion with goals of 75% “some” homework completion. Safety will be assessed throughout the study as described in Section 8.2. Iterative adaptation and refinement will optimize achievement of feasibility goals.

Acceptability will be determined by qualitative analysis of individual interviews at the end of treatment to elicit perceptions about treatment content (utility, appropriateness) and format (convenience, number and length of sessions). We will also use the Treatment Evaluation Inventory. Total scores range from 9-45. Scores ≥ 27 indicate “moderate” treatment acceptability(38). Descriptive statistics (means, standard deviations), frequency counts, and percentages will characterize treatment satisfaction and primary and secondary outcomes. We will use the qualitative analytic approach described in Section 9.4.1 to identify key themes from interviews and optimize I-STRONG for testing in a randomized clinical trial.

Exploratory Analysis. Descriptive statistics including means, standard deviations, frequency counts, and percentages will characterize performance-based measures (6-minute walk test) and healthcare utilization per medical chart review.

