Research coordinators and assistants will complete and maintain CITI certification and undergo training to use REDCap for data collection and management. The PI will train research personnel in the process of screening eligible participants, recruitment, and the consenting process. Research personnel also will receive standardized training on the administration and scoring of measures using REDCap as well as paper-pencil measures. The research staff also will be trained in a specific procedural plan for identifying potential psychological distress and contacting a psychologist (Drs. [name], [name]) to conduct follow-up assessment at the site of data collection. Research team members will be trained in conducting semi-structured individual interviews to ensure scientific rigor and consistency. Professional transcription services will be utilized for transcription. Members of the Emory Qualitative Research Core will complete coding of qualitative data under the supervision of the PI and qualitative methods expert ([name]).

26. Multi-Site Research When Emory is the Lead Site

Study-Wide Number of Participants

Up to 45 adolescents and their caregivers will be accrued across sites. This includes approximately 15-20 dyads for qualitative interviews or until saturation of themes is achieved, 8 patients and 8 caregivers for stakeholder advisory board, and 15 dyads for the feasibility study. Additional dyads may be recruited to optimize feasibility and acceptability.

Study-Wide Recruitment Methods

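### The Aim 2 enrolment goal is at least 75% in Section 2 but at least 30% in Section 18, so a consent rate from 30% to just under 75% meets one goal and misses the other

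*Combined protocol and SAP*

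**What the plan says.** Section 2 (Objectives, Aim 2) names three rates and attaches one figure to them: "Feasibility will be demonstrated by rates of study enrollment, retention, and adherence (target goals set at" 75% or more). It gives no denominator for the enrolment rate.

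Section 18 (Data Analysis, Aim 2 Feasibility and Acceptability) supplies the only definition of that rate: "enrollment (percent of eligible participants that consent". It then introduces a list of goals with "We anticipate with iterative refinement to achieve the following target goals". The first is that 30% or more "of eligible patients approached will consent". The others are 75% or more for retention, 90% or more for completion of primary outcome assessments at the 3-month follow-up, and 75% or more for treatment completion. A further goal of 75% applies to completing at least some homework.

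Both sections are current text. Neither refers to the other's figure, and no order of precedence is given.

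**The concern.** Assessing feasibility is the stated question of Aim 2, and Section 2 says these rates will demonstrate it. A rate judged against a goal needs one goal. Here a moderate consent rate of 40%, 50% or 60% could be reported as on target by citing Section 18 or as short of target by citing Section 2.

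The observed rate will be reported either way; what is undetermined is the benchmark beside it. If that is settled only after the rate is known, the choice can follow the result. Section 18 says the study is meant to prepare the intervention for a randomized trial, so whether recruitment met its goal is information the next stage will use.

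**Working it through.** **Step 1: compare the goals rate by rate.**

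| Rate | Section 2 | Section 18 | Agree? |
|---|---|---|---|
| Enrolment | ≥75% | ≥30% of eligible patients approached | No |
| Retention | ≥75% | ≥75% | Yes |
| Adherence | ≥75% | ≥75% treatment completion; 75% for some homework | Yes, in figure |
| Primary outcome assessments | not named | ≥90% | No conflict |

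The adherence row matches because Section 6 defines adherence by two parts: "Adherence to treatment will be assessed based on patient attendance at treatment sessions and patient self-report of home practice". Section 18 has a 75% goal for each part. Only enrolment conflicts.

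**Step 2: the range of disagreement.** The gap is 75 − 30 = 45 percentage points. For a consent rate p:

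- p ≥ 75%: both goals met
- 30% ≤ p < 75%: Section 18 met, Section 2 missed
- p < 30%: both missed

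**Step 3: what this means in patients.** The documents plan no number to be approached, so this step is illustrative. For n enrolled, the largest number approached that still meets a target t is floor(n / t).

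The documents allow several values of n. Section 2 gives 12 adolescents and Section 12 approximately 12 dyads. Section 26 gives "15 dyads for the feasibility study". Section 6 says "We will conduct 2-3 groups of 4-6 patients in each group", which spans 2 × 4 = 8 to 3 × 6 = 18.

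| n enrolled | floor(n / 0.75) | floor(n / 0.30) | Sections disagree at (approached) | Consent rate over that range |
|---|---|---|---|---|
| 8 | 10 | 26 | 11 to 26 | 72.7% to 30.8% |
| 12 | 16 | 40 | 17 to 40 | 70.6% to 30.0% |
| 15 | 20 | 50 | 21 to 50 | 71.4% to 30.0% |
| 18 | 24 | 60 | 25 to 60 | 72.0% to 30.0% |

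Edge checks for 12 enrolled: 12/16 = 75.0% meets both goals; 12/17 = 70.6% and 12/40 = 30.0% meet only the Section 18 goal; 12/41 = 29.3% meets neither.

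No power, alpha or sample-size figure is involved, so there is none to reproduce.

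**The case against.** The strongest reply is that the two sections may not measure the same thing. Section 2 speaks only of an enrolment rate, without a denominator, and its parenthesis could be read as applying to adherence alone. The missing denominator is a fair point, and applying 75% to the consent rate is an inference. It is the natural one: the goals are in the plural after a list of three rates, Section 18 gives retention the same 75%, and the only enrolment rate defined for Aim 2 is the consent rate. If something narrower was meant, the Section 2 sentence still needs editing.

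A second reply is that little depends on it. Section 18 is the analysis section and sets a goal for each metric, so an analyst would probably work from it. The goals are worded as anticipated results of iterative refinement, the analysis is descriptive, and the Section 4 list of Aim 2 endpoints does not name enrolment. This limits the consequence: no estimate, sample size or safety rule is affected. It does not remove the conflict. The Section 4 list is not exhaustive, and Sections 2 and 18 both treat enrolment as a feasibility measure.

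Nor do the 80-95% recruitment rates in Section 13 settle the matter. They concern qualitative interviews, not the Aim 2 intervention.

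**Conclusion.** The concern holds. The plan states two enrolment goals for Aim 2, 45 percentage points apart, and they give opposite answers for any consent rate from 30% to just under 75%. With the 12 participants planned in Section 2, that is 17 to 40 patients approached.

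This rests on reading the Section 2 figure as covering all three listed rates and on taking enrolment there to be the consent rate defined in Section 18. The counts also depend on how many enrol; the percentage range does not. This should be fixed, but it is a conflict in a descriptive benchmark and has no bearing on error rates or power.

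**What to change.** Before the Aim 2 consent rate is known, the sponsor should choose one enrolment target and state it in Sections 2 and 18. The documents do not show which figure was intended. If it is the Section 18 figure, Section 2 could read: *enrollment ≥30% of eligible patients approached; retention and adherence ≥75%*. Keep the word adherence, because Section 6 gives it a wider meaning than attendance. If it is 75%, change the Section 18 enrolment goal instead.

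As a tidy-up, use eligible patients approached as the denominator for both the enrolment metric and its target in Section 18; the definition now refers to eligible participants. Section 13 already plans the counts: "We will track the number of eligible patients screened by phone or in-person, enrolled, and reasons for refusal". It counts patients screened rather than approached, but it also says all potentially eligible patients will be approached and screened at routine visits. The tally sheet need only make clear who counts as approached.

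The cost is one sentence and one phrase, with no new data collection expected. Section 26 requires modifications to be approved at each site before they are implemented. Keeping 30% makes the Section 2 goal less ambitious; keeping 75% makes the Section 18 goal harder to reach.

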Patient Global Impression of Change (PGIC)	Overall rating of efficacy of treatment(28) (T)	X		X	X
Treatment Evaluation Inventory	Treatment acceptance and satisfaction (T, P)(38)			X	X
Tampa Scale of Kinesiophobia	Fear of movement related to fear of pain(39) (T)		X	X	X
Exploratory outcome measures					
6-minute walk test	Distance patient can walk over a total of six minutes on a hard, flat surface (T)(40)		X		X
Physical activity via actigraphy	Peak and Total daily physical activity, categorized into light, moderate, and vigorous activity(41, 42)		X		X
Healthcare utilization	Total # ED visits, admissions for pain for 6-months via medical chart review in compliance with HIPPA		X		X

I-STRONG Intervention. In addition to usual care, youth will receive the I-STRONG intervention consisting of 16 group-based telehealth sessions (90 min/session) held twice per week over 8 weeks. Group size will vary with up to 4-6 patients with SCD per group, which was found to be the ideal group size based on our pilot work. Parents will be included in at least 6 of the 16 sessions and will receive education about I-STRONG, instruction on how to support teen behavior change to enhance generalizability at home, and have opportunities for social support and networking with other parents of youth with SCD. Participants will have the opportunity to interact with other participants during group sessions as well as two shared interventionists (a behavioral coach and movement coach). As is common for behavioral interventions in clinical trials, treatment completion is defined as attending at least 75% of sessions.

The intervention will be delivered jointly by a behavioral health coach (e.g., doctoral-level psychology provider) and movement training coach (e.g., trained physical therapist, exercise physiologist) using a restricted password-protected, HIPPA compliant audio-video virtual platform (e.g., Zoom Business). As described in Table 2, the behavioral health coach will deliver mind-body and cognitive-behavioral strategies for the first 30 mins of each session to reduce

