Patients and parents may elect to receive aggregate data on the study findings at the completion of the study (e.g., via study newsletter, email, or mailed letter).

8. Study Timelines

Aim 1. Patients and parents who provide consent/assent for Aim 1 will participate up to 6 months (between 1-6 study visits). Patients and parents who only complete the qualitative interview will participate for 1 study visit; patients and parents who are part of the stakeholder advisory boards will participate for up to 6 study visits.

Aim 2. Patients and parents who provide consent/assent for Aim 2 will participate up to 5 months (20 study visits), including 3 study assessments, 16 intervention sessions, 1 booster session, and qualitative exit interview combined with post-treatment assessment.

9. Inclusion and Exclusion Criteria

Inclusion criteria:

- (a) 12-18 years old (the developmental period when chronic pain is prevalent among youth (44)),
- (b) diagnosed with SCD (any genotype),
- (c) score at least 3 (indicating medium to high risk for chronic pain) on the Pediatric Pain Screening Tool (29, 45).
- (d) stable disease-modifying treatments, if applicable, as defined by no newly initiated or significantly increased dosages (mg/kg) in the past 3 months (Aim 2 only)
- (e) English fluency (Aim 2 only)

Exclusion criteria:

- (a) comorbid medical conditions typically associated with pain but unrelated to SCD (e.g., rheumatologic disorders or inflammatory bowel disease);
- (b) significant cognitive or developmental limitations, as per their healthcare provider or parent, which would impair completion of self-report measures or engagement in mind-body interventions.
- (c) presence of a condition(s) or diagnosis, either physical or psychological, or physical exam finding that precludes participation (e.g., severe avascular necrosis with limited or non-weight bearing restrictions, significant cognitive or developmental limitations, active suicidal ideation) (Aim 2 only)
- (d) Adolescent receiving active treatment (e.g., weekly appointments with a provider) for nonpharmacological therapies (e.g., structured behavioral pain management, physical therapy, or acupuncture program) that overlap with the active phase of the study intervention (Aim 2 only)

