Objective measures of physical activity via actigraphy will be characterized by descriptive statistics, including frequency counts, percentages, means, and standard deviations. Feasibility metrics will include participant adherence to wearing the actigraphs (e.g., percent of time during the day, percent of days per week). A “complete” day of data will be defined as ≥ 80% of monitor-wearing time. Descriptive statistics will characterize average activity counts per minute during daytime hours, peak activity, and average time (in minutes) spent in sedentary, light, moderate, and vigorous activity per day during daytime hours.

19. Provisions to Monitor the Data to Protect the Safety of Participants

We recognize the need to provide a plan to ensure the scientific integrity and safeguard the well-being of study participants. The study team is highly qualified to lead the qualitative interviews and behavioral intervention. All study interventionists will be trained to conduct the interventions using a manualized protocol and will monitor the comfort and safety of participants at each session. The PI and study interventionists will have regular monthly meetings to discuss the progress of the study, the integrity of the treatment delivery, and discuss any adverse events.

Internal monitoring of the trial for protocol compliance and data accuracy will be the responsibility of the Research Administration QA/QI Analyst. The trial will be monitored for completion of the informed consent forms, clinical data capture forms, IP dispense logs and treatment-related adverse events not related to SCD. In addition, the credentials, delegation of authority and training logs will be monitored for study member. The monitoring will occur according to the following schedule:

- At least every six months while participants are receiving intervention and
- Annually while participants are in follow-up
- Close-Out Study Visit

Additional monitoring may be performed in the event of Serious Adverse Events if deemed necessary by the monitoring committee or if requested by the Principal Investigator.

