Real-time review of participant data during initial data collection.	Inclusion/Exclusion Checklist is completed by the CRC via RedCap	This is completed when patients enroll	Study team and PI
100% review of regulatory files	Regulatory binder will be created to house all Regulatory documents for review. Regulatory files will be reviewed by monitor at monitoring visits.	Start of study, close out and as necessary in between	Team coordinators, QA/QI Analyst
100% review of consent forms	Per Aflac policy, all consents are reviewed in real time by 2 separate coordinators. The first review is within 5 days of the consent. The next review is within 5 days of the first review but within 10 days of the consent date. Consents will be reviewed by monitor at monitoring visits.	As consents are signed	Team coordinators, QA/QI Analyst
Review of credentials, training records, the delegation of responsibility logs (if applicable)	Study training logs are kept in the Regulatory Binder for review with the upkeep of the coordinators. This information will be reviewed by monitor at monitoring visits.	Reviewed every time there is a new staff added to the study as well as study amendments	Team coordinators, QA/QI Analyst

Protocol Title: Integrative Training Program for Pediatric Sickle Cell Pain

Comparison of case report forms (CRF) to source documentation for accuracy and completion	Data will be stored via Redcap. CRF documentation will be reviewed by monitor at monitoring visits.	Yearly Review	Principal Investigator, QA/QI Analyst
Review of documentation of all adverse events	The PI will have oversight on the documentation of AE's which will be logged and tracked by the study Coordinator and kept in the subject's chart. AE documentation will be reviewed by monitor at monitoring visits.	Every time an AE occurs the Study Coordinator will log it. Monitor will review at specified monitoring intervals.	Principal Investigator, Team Coordinators, and QA/QI Analyst

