Monitoring of critical data points (eligibility, study endpoints, etc.)	Data Collection and data points is captured via RedCap and is the responsibility of the study coordinators under the supervision of the principal investigator to make sure all questionnaires are completed. The coordinators are responsible for ensuring accuracy, completeness, legibility, and timeliness of the data reported. The PI will have oversight over all data collected for the study. The monitor will review critical data points at monitoring visits. The PI will review all monitoring reports upon the completion of a monitoring visit.	Eligibility will be done at time of patient enrollment. Study endpoint will be reviewed at end of each treatment period	Principal Investigator and Team Coordinators, and QA/QI Analyst
For FDA regulated studies, the following requirements apply:	How this Requirement is Met	Timing, frequency, and intensity of monitoring	Responsible Party(ies)
Monitoring methods (may include centralized, on-site, and self-monitoring)	The QA/QI Analyst will be monitoring this study going forward.	As per protocol	QA/QI Analyst

*For international studies, you are required to engage a CRO that is working in the site country and/or to consult with Emory's legal counsel regarding compliance with the country's clinical research regulations.

20. Provisions to Protect the Privacy Interest of Participants

General: To help reduce any uneasiness or discomfort about answering questions about their health, the research protocol includes standardized measures that have been widely used in other research of youth in this age range with SCD without adverse effects. Participants will be allowed to skip any questions that they do not feel comfortable answering and will have opportunities for breaks to minimize fatigue. Participants will be informed of their right to terminate their participation in any part of data collection at any time and will be given phone numbers of the PI as well as the IRB if they would like to issue a complaint or desire any additional information regarding the study.

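### Does the narrower adverse event wording in the Section 19 narrative let sickle cell pain events escape monitoring or reporting?

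*Combined protocol and SAP*

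**What the plan says.** Section 19 of the protocol speaks twice about adverse event monitoring. The narrative makes the Research Administration QA/QI Analyst responsible for internal monitoring and lists what is checked: consent forms, data capture forms, and "IP dispense logs and treatment-related adverse events not related to SCD". The table that follows has a row headed "Review of documentation of all adverse events". In that row the investigator oversees documentation, the monitor reviews it at monitoring visits, and the QA/QI Analyst is among the responsible parties. On logging, the row says "Every time an AE occurs the Study Coordinator will log it". A later row confirms who the monitor is: "The QA/QI Analyst will be monitoring this study going forward".

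Section 18 describes the Aim 2 analysis as descriptive. It lists enrollment, retention, assessment and treatment completion, homework, acceptability, primary and secondary outcomes, the 6-minute walk test, utilization and actigraphy. Its one sentence on safety is "Safety will be assessed throughout the study as described in Section 8.2". The heading of Section 8 is "8. Study Timelines", and that section has no subsections. Pain-related hospital contact does appear: the questionnaire table in Section 6 includes "Total # ED visits, admissions for pain for 6-months via medical chart review", and the exploratory analysis in Section 18 summarises "healthcare utilization per medical chart review".

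**The concern.** The two scopes differ on an event that matters here. All Aim 2 adolescents have SCD and do progressive movement training. If a session provokes a sickle cell pain episode, that episode is related both to treatment and to SCD. Read literally, the narrative does not name it; the table includes it. A monitor working from the narrative alone might pass over it.

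The protocol also relies on this kind of event as evidence of safety. Section 3 says the parent program did not worsen pain, and Section 15 says participants so far have had no flares. Aim 2 prepares the intervention for a randomized trial, so a reader would want a comparable count at its end. Yet Section 18 plans none, its safety reference leads nowhere, and no supplied text says whether an SCD pain episode is an adverse event. With two sites and about 12 participants, inconsistent handling could change the picture.

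**Working it through.** The plan gives no figure to reproduce. The check compares the texts, then asks which numbers could depend on the difference.

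**Step 1: scope.** Classify events by two yes/no attributes, giving 2 × 2 = 4 classes.

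| Treatment-related | SCD-related | Named in narrative | Covered by table |
|---|---|---|---|
| Yes | No | Yes | Yes |
| Yes | Yes | No | Yes |
| No | No | No | Yes |
| No | Yes | No | Yes |

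The narrative names 1 of 4 and the table covers 4 of 4. The union is 4 of 4. The narrative does not say that only its class is monitored, so the two can both be met by following the table. A conflict appears only if the word *only* is read into the narrative.

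**Step 2: what the narrative governs.** It concerns an internal check of compliance and data accuracy. It does not say what is logged. The table sets the logging rule, and that rule has no filter for relatedness or for SCD. A count of events, or of participants with an event, would be taken from the log. Changing the narrative would leave that count the same.

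**Step 3: other routes by which an event would surface.** Section 19 has interventionists watching comfort and safety at each session, monthly meetings that discuss adverse events without restriction, possible extra monitoring after serious events, and a seven-member DSMB that reviews study results quarterly. Section 20 makes site hematologists available for pain arising from the movement training.

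**Step 4: the sizes one might attach.** Section 12 plans about 12 dyads and Section 26 gives 15. One participant's classification moves the share with any event by 1/12 = 8.3 points or 1/15 = 6.7 points. Section 6 allows 2 to 3 groups of 4 to 6, so 2 × 4 = 8 to 3 × 6 = 18 participants, and the shift could lie between 1/8 = 12.5 and 1/18 = 5.6 points. This holds only if that participant has no other event. It follows from whether a pain episode is called an adverse event, and the narrative sentence does not decide that.

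**Step 5: what a summary could show.** With no events, the exact two-sided 95% upper limit is 1 − 0.025^(1/n). For n = 12 it is 26.5%; for n = 15 it is 21.8%. A table of this size is descriptive and would support no firm statement on harm.

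**Step 6: the reference.** Section 18 also cites a Section 9.4.1 for the qualitative approach. Section 9 holds the eligibility criteria and has no such subsection. Two dead references in one passage suggest text carried over from a differently numbered document. That is an inference, but it fits a slip better than a missing safety plan.

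**The case for a change.** The strongest case for a change does not need a contradiction. It says that a protocol which offers absence of pain flares as safety evidence should state whether such flares count as adverse events, who judges relatedness, and how they will be summarised. Without a rule, two sites could log the same episode differently, and a later count from the log would inherit that difference. The pain measures do not fill the gap: the Brief Pain Inventory at three time points and the one-week diary cannot tie an episode to a session, and chart-reviewed visits miss episodes managed at home. The remedy would cost a few lines of text.

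Part of this stands. The status of SCD pain episodes is not stated in the supplied text, and Section 18 has no adverse event line. But these are gaps in detail, and widening the narrative would not close them. Participants are selected for chronic-pain risk, so some pain is expected from the disease. Whether and when an episode beyond baseline counts is for the investigators to define. Adding all SCD pain episodes to the monitored list without that definition would leave the between-site difference where it was. The adverse event form, manuals and appendices were not supplied, so the absence of a classification rule cannot be taken as established. Pain worsening is also not left to interviews alone: pain severity is the primary outcome, interference, analgesic use and global impression of change are secondary, and Section 18 plans descriptive summaries of them.

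**Conclusion.** The wording differs, but nothing is shown to be lost. The broader provision in the table covers every attribution class, logging is unrestricted, and other oversight runs alongside it. The effect of the narrative sentence on any reported count is nil, because counts come from the log. The 8.3 and 6.7 point figures belong to a separate question of classification and should not be charged to this sentence.

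The absence of a planned adverse event table is an omission that an analyst of a small single-arm feasibility study would fill by reporting events and participants affected from the log. The reference to Section 8.2 is clerical, as is the one to Section 9.4.1. Both, and the mismatch of wording, are housekeeping for whenever the text is next opened, and none bears on the design or the analysis.

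This rests on three assumptions: that staff follow the table's logging and review row as written; that the unsupplied form or manual, or the investigators, settle how pain episodes are classified at both sites; and that the narrative is read as a list of items checked, not as a limit. If the table were not followed, the conclusion would weaken, but the documents give no sign of that.
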